## 4. Trial population

### 4.1. Screening data

Screening data will be based on patients that are defined as eligible by the clinical and research team. Screening will be performed in three phases:

- (i) Screening based on the eligibility criteria (see ‘4.2 Eligibility’) by the clinicians/surgeons of the research team.
- (ii) Screening based on phone call by the research team.
- (iii) Screening during the baseline assessment.

The number of participants in each phase will be reported.

### 4.2. Eligibility

Eligible patients will be defined based on the inclusion and exclusion criteria. In general, colon cancer patients, older than 40 years old, undergoing a surgical procedure will be considered for eligibility. Specific inclusion and exclusion criteria are:

#### Inclusion criteria:

1. Patients older than 40 years old.
2. Diagnosis of nonmetastatic colon cancer (i.e., including right, transverse, left, sigmoid, subtotal, total and hemicolectomy).
3. Not participating in a nutritional/dietary intervention.
4. Being physical inactive (i.e., not to be participating in any physical exercise program in the last 3 months or performing less than 600 metabolic equivalents (METS)/week of moderate-vigorous physical activity).
5. To be capable and willing to provide informed consent.
6. Not to suffer from any specific condition that may impede testing the study hypothesis or make it unsafe to engage in the multidisciplinary intervention.

#### Exclusion criteria:

1. Medical contraindication for being engaged in an exercise or dietary program.
2. Additional surgery planned within the 3-month intervention.
3. History of another primary invasive cancer.
4. Planning to receive adjuvant chemotherapy.
5. To be pregnant.

6. To present any of the following clinical condition: (i) myocardial infarction or coronary revascularization procedure within prior 3 months; (ii) uncontrolled hypertension (i.e., systolic  $\geq$  180 mmHg or diastolic  $\geq$  100 mmHg); (iii) uncontrolled arrhythmias; (iv) valvular disease clinically significant; (v) decompensated heart failure or (vi) to suffer from known aortic aneurysm.

#### 4.3. Recruitment

Information concerning the CONSORT flow diagram will be collected. During the enrolment phase, we will record the number of patients assessed for eligibility, those excluded (with the specific reason), and the total number of participants randomized. In the allocation phase, we will report the number of participants in each group, as well as those who received or not the allocated intervention. During the follow-up, we will report the number of participants who lost to follow-up and the number who discontinued (plus reason). Finally, the number of participants included in the final analyses will be described.

#### 4.4. Withdraw/follow-up

The number and reason of withdraw will be collected and reported by the research team.

#### 4.5. Baseline patients' characteristics

A baseline table will be created to describe the characteristics of the study population. The characteristics include general characteristics (e.g., age or sex), anthropometry and body composition (e.g., body weight, height, body mass index or waist circumference), cardiometabolic health (e.g., glycaemic or lipid profile), physical fitness (e.g., cardiorespiratory fitness or muscular strength), tumour stage and surgery characteristics (e.g., type of surgery or duration of surgery). The characteristics of the total study population and each study arm will be summarized using mean (SD) or median (interquartile range) for normally and not normally distributed continuous variables, respectively, and as number (percentage) for categorical variables.

## 5. Analysis

### 5.1. Outcomes definition

#### Primary outcomes

**CCI** obtained by patients at 30 days and 3 months after the surgical procedure.

#### Secondary outcomes

1. **CCI** scores obtained at 1 year post-surgery.
2. **Proportion of patients experiencing at least one complication** within 30 days, 3 months and 1 year post-surgery.
3. **Proportion of patients experiencing at least one medical complication** within 30 days, 3 months and 1 year post-surgery.
4. **Proportion of patients experiencing at least one surgical complication** within 30 days, 3 months and 1 year post-surgery.
5. **Hospital readmissions occurring** within 30 days, 3 months and 1 year post-surgery.
6. **Urgency visits** within 30 days, 3 months and 1 year post-surgery.
7. **Hospital length of stay**, defined as the total number of days the patient remains admitted in the hospital following the surgical procedure.
8. **Quality of Recovery Short-form Questionnaire (QOR-15)** measured 24, 48 and 72 hours after the surgical procedure.
9. **Change in body weight** (Baseline, preoperatively, 3 months after surgery and 1 year after surgery). Body weight will be measured by a digital scale.
10. **Change in body height** (Baseline, preoperatively, 3 months after surgery and 1 year after surgery). Body height will be measured by a stadiometer.
11. **Change in fat mass** (Baseline, preoperatively, 3 months after surgery and 1 year after surgery). Fat mass will be assessed by Dual-energy X-ray Absorptiometry (DXA).
12. **Change in fat free mass** (Baseline, preoperatively, 3 months after surgery and 1 year after surgery). Fat free mass will be assessed by Dual-energy X-ray Absorptiometry (DXA).
13. **Change in bone mineral density** (Baseline, preoperatively, 3 months after surgery and 1 year after surgery). Bone mineral density will be assessed by Dual-energy X-ray Absorptiometry (DXA).
14. **Change in waist circumference** (Baseline, preoperatively, 3 months after surgery and 1 year after surgery). Waist circumference will be measured following the procedures outlined by the International Society for the Advancement of Kinanthropometry.
15. **Change in hip circumference** (Baseline, preoperatively, 3 months after surgery and 1 year after surgery). Hip circumference will be measured following the procedures outlined by the International Society for the Advancement of Kinanthropometry.
16. **Change in neck circumference** (Baseline, preoperatively, 3 months after surgery and 1 year after surgery). Neck circumference will be measured following the

procedures outlined by the International Society for the Advancement of Kinanthropometry.

17. **Change in systolic blood pressure** (Baseline, preoperatively, 3 months after surgery and 1 year after surgery). Systolic blood pressure will be assessed by blood pressure monitor.
18. **Change in diastolic blood pressure** (Baseline, preoperatively, 3 months after surgery and 1 year after surgery). Diastolic blood pressure will be assessed by blood pressure monitor.
19. **Change in cardiorespiratory fitness** (Baseline, preoperatively, 3 months after surgery and 1 year after surgery). Cardiorespiratory fitness will be measured by the distance done in 6 minute walking test.
20. **Change in upper limb muscular strength** (Baseline, preoperatively, 3 months after surgery and 1 year after surgery). Upper limb muscular strength will be measured using a digital hand dynamometer.
21. **Change in lower limb muscular strength** (Baseline, preoperatively, 3 months after surgery and 1 year after surgery). Lower limb muscular strength will be assessed by the 30 seconds sit-to-stand test.
22. **Change in lower limb muscular strength** (Baseline, preoperatively, 3 months after surgery and 1 year after surgery). Lower limb muscular strength will be assessed by the 5 times sit-to-stand test.
23. **Change in gait speed** (Baseline, preoperatively, 3 months after surgery and 1 year after surgery). Gait speed will be determined by the 4-meter usual gait speed test.
24. **Change in Health-related quality of life** (Baseline, preoperatively, 3 months after surgery and 1 year after surgery). Health-related quality of life will be assessed through The European Organisation for Research and Treatment of Cancer quality of life questionnaire for patients with colorectal cancer (EORT-QLQ-CR29).
25. **Change in self-reported depression levels** (Baseline, preoperatively, 3 months after surgery and 1 year after surgery). Self-reported depression levels will be measured by Back Depression Inventory-II questionnaire and Hospital Anxiety and Depression Scale.
26. **Change in self-reported anxiety levels** (Baseline, preoperatively, 3 months after surgery and 1 year after surgery). Self-reported anxiety levels will be measured by State-Trait Anxiety Inventory and Hospital Anxiety and Depression Scale.
27. **Change in mental adjustment to cancer** (Baseline, preoperatively, 3 months after surgery and 1 year after surgery). Mental adjustment to cancer will be assessed using the Mini-Mental Adjustment to Cancer questionnaire.
28. **Change in glycaemic profile** (Baseline, preoperatively, 3 months after surgery and 1 year after surgery). Blood samples will be used to assess glucose and insulin levels.
29. **Change in lipid profile** (Baseline, preoperatively, 3 months after surgery and 1 year after surgery). Blood samples will be used to assess total cholesterol, HDL-Cholesterol, LDL-cholesterol and triglycerides levels.

30. **Change in immunological blood profiles** (Baseline, preoperatively, 3 months after surgery and 1 year after surgery). Blood samples will be used to assess Leukocytes ( $10^3$  uL), Neutrophils ( $10^3$  uL), Lymphocytes ( $10^3$  uL), Monocytes ( $10^3$  uL), Eosinophils ( $10^3$  uL), Basophils ( $10^3$  uL) and LUC cells ( $10^3$  uL).
31. **Change in inflammatory factors** (Baseline, preoperatively, 3 months after surgery and 1 year after surgery). Blood samples will be used to assess C-Reactive protein, leptin, adiponectin, resistin, IL-6, IL-10
32. **Change in renal function parameters** (Baseline, preoperatively, 3 months after surgery and 1 year after surgery). Blood samples will be used to assess creatinine and urea.
33. **Change in tumour markers** (Baseline, preoperatively, 3 months after surgery and 1 year after surgery). Blood samples will be used to assess CA19-9, CA 242, CA 72-4 and CEA.
34. **Change in hormones** (Baseline, preoperatively, 3 months after surgery and 1 year after surgery). Blood samples will be used to assess T3, T4, testosterone, cortisol, oestrogens and DHEAs.
35. **Change in energy intake** (Baseline, preoperatively, 3 months after surgery and 1 year after surgery). Energy intake (kcal/day) will be assessed by food frequency questionnaire (FFQ).
36. **Change in carbohydrates intake** (Baseline, preoperatively, 3 months after surgery and 1 year after surgery). Carbohydrates intake will be assessed by FFQ.
37. **Change in fat intake** (Baseline, preoperatively, 3 months after surgery and 1 year after surgery). Fat intake will be assessed by FFQ.
38. **Change in protein intake** (Baseline, preoperatively, 3 months after surgery and 1 year after surgery). Protein intake will be assessed by FFQ.
39. **Change in dietary habits** (Baseline, preoperatively, 3 months after surgery and 1 year after surgery). Dietary habits will be assessed by food frequency questionnaire (FFQ).
40. **Change in subjective sleep quality** (Baseline, preoperatively, 3 months after surgery and 1 year after surgery). Subjective sleep quality will be assessed by the Pittsburgh Sleep Quality Index (PSQI).
41. **Change in objective sleep quality** (Baseline, preoperatively, 3 months after surgery and 1 year after surgery). Subjective sleep quality will be assessed by accelerometry.
42. **Change in physical activity patterns** (Baseline, preoperatively, 3 months after surgery and 1 year after surgery). Physical activity patterns will be assessed by accelerometry.
43. **Change in faecal microbiota composition and diversity** (Baseline, preoperatively, 3 months after surgery and 1 year after surgery). Faecal microbiota composition and diversity will be determined by DNA sequencing.
44. **Change in heart rate variability** (Baseline, preoperatively, 3 months after surgery and 1 year after surgery). Heart rate variability will be measured with the

participant lying in a supine position, with R–R signal being assessed for 15 min using the Polar Ignite 2.

45. **Tumour tissue analyses.** Colon tissue will be collected during the surgical procedure.

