### 2.3. Sample size

In a previous study, a 17.3-point mean difference was detected in CCI between a group of patients who were physically inactive and a group who were regularly active, both undergoing colorectal cancer surgery (2). Therefore, this study sample size was estimated for an  $\alpha$  level of 0.05 and 90% power to detect a 17.3-point difference in CCI (primary outcome) between usual care and PPP groups, considering an  $\sigma$  of 25.2 (the CCI standard deviation of the group of participants who were physically inactive). Based on this data, a sample of 36 participants per group was considered sufficient for our analysis. However, assuming a 20% drop-out rate, we decided to recruit a total sample size of 45 participants for each study group. Thus, a total of 90 participants ( $n \approx 45$  women) will be enrolled in the ONCOFIT study.

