## 3. Statistical principles

### 3.1. Confidence and P values

All statistical tests will be two-tailed, with a significance level set at  $\alpha = 0.05$ . Corresponding 95% confidence intervals will be reported. No adjustments for multiplicity will be applied, as only one primary outcome has been pre-specified and all secondary and exploratory analyses are considered hypothesis-generating.

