### 3.3. Analysis population

We plan to use two analyses approaches:

- (i) Intention-to-treat: This dataset will be used for the primary analysis of all outcomes and will include all the randomized participants. They will be analyzed based on the group they were originally allocated.
- (ii) Per-protocol analyses: This dataset will be used for secondary analyses and will include participants with >80% of attendance.

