### 5.2. Analyses methods

The main analyses for primary and secondary outcomes will follow the intention-to-treat approach. For the primary outcome, given the commonly observed non-normality distribution of the data in this fields, a Mann-Whitney U test will be used to compare the median CCI between the intervention and control groups. For secondary outcomes with a single time-point (e.g., hospital lenght of stay), comparisons between groups will also be conducted using Mann-Whitney U test. To assess whether the group allocation (intervention/control) influences the risk of postoperative complications (yes/no), a binary logistic regression model will be conducted. Regarding secondary outcomes at multiple time points, a linear mixed-effects models with individual measures of growth being modelled as the function of randomly assigned group, assessment time, and the interaction between group and time. Estimations will be performed using the restricted maximum-likelihood method, including an unstructured covariance matrix to adjust for within-participant clustering resulting from the repeated-measures design. This model will assume that missing values are missing-at-random.

Secondary analyses will be performed using the per-protocol approach, defined as attending >80% of the sessions offered to the intervention group.

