### 5.3. Missing data

The number of missing data will be reported, and patterns of missing data will be explored. Based on previous experience, no missing data are expected for prognostic variables, as these will be extracted from medical records and used unless the patient explicitly revokes consent. For other outcomes, we expect that missing data will be assumed as missing at random. Therefore, the linear mixed model analyses will appropriately account for missing data. Nonetheless, once data processing has been completed, we will formally re-evaluate this assumption.

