#### 5.5. Harms

The number and reasons of adverse events (e.g., falls, injuries, musculoskeletal problems, major cardiovascular disease events, or any other events potentially related to the implementation of the trial protocol) at each time point will be collected, reported, and described separately for each study arm. No formal statistical testing will be undertaken.

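### Length of stay has no rule for in-hospital death, so the planned Mann-Whitney comparison would rank an early death as a short, favourable stay

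*SAP*

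**What the plan says.** Four parts of the SAP together fix how an in-hospital death would be handled.

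- **Definition (5.1, Secondary outcomes, item 7).** Length of stay is "defined as the total number of days the patient remains admitted in the hospital following the surgical procedure". The count ends when the admission ends, for whatever reason.
- **Test (5.2).** The rule opens "For secondary outcomes with a single time-point (e.g., hospital lenght of stay" and goes on to say that "comparisons between groups will also be conducted using Mann-Whitney U test". Length of stay is the section's own example of this class of outcome.
- **Population (3.3).** The intention-to-treat set is the primary set for all outcomes and "will include all the randomized participants".
- **Missing data (5.3).** Because the source is the medical record, "no missing data are expected for prognostic variables".

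The SAP mentions neither death nor mortality. It has no worst-rank rule, no discharged-alive condition, no competing-event method and no exclusion. Section 5.5 describes adverse events by arm, does not name death among its examples, and states that "No formal statistical testing will be undertaken".

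**The concern.** Length of stay is one of the clinical prognosis outcomes behind secondary aim (i), where a shorter stay will be read as a better recovery. A patient who dies on day 3 has a recorded stay of about 3 days. Under the sections above, that value is valid, is not missing, belongs to an included patient, and takes one of the lowest ranks. The ordering of patients is then wrong for the use to which the outcome is put: the worst result sits next to the best ones, and the arm with an early death looks slightly better because of it.

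Timing matters too. If the handling of deaths is settled only once the arm in which they occurred is known, the choice is open to the charge of being data-driven.

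**Working it through.** **Inputs.** The SAP gives no figure for length of stay or for mortality, so it has no result of its own to reproduce on this point. The one figure used is 45 patients per arm (section 2.3), which follows from 36/(1 − 0.20) = 45. Section 2.2 specifies simple randomization, so exactly equal arms are an approximation. Tests are two-sided at 0.05 (section 3.1). The number of deaths, their timing and their split between arms are assumptions.

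**Step 1: scale of the test.** Let P = U/(n·m), the estimated probability that a patient in one arm stays longer than a patient in the other. Its value under no difference is 0.50. With n = m = 45 and no tie correction,

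SE₀ = √[(n + m + 1)/(12·n·m)] = √[91/(12 × 45 × 45)] = √(91/24,300) = 0.0612.

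Stays in whole days will produce ties, which make the standard error slightly smaller, so the z values below are approximate.

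**Step 2: effect of re-scoring one death.** Suppose the recorded stay of the patient who died exceeds a fraction f of the stays in the other arm. Moving that patient to the worst rank changes P by (1 − f)·45/2025 = (1 − f)/45.

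| Timing of death | f | Change in P | Change in z |
|---|---|---|---|
| Very early, shorter than every stay in the other arm | 0 | 0.0222 | 0.0222/0.0612 = 0.36 |
| At about the median stay | 0.5 | 0.0111 | 0.18 |
| After a very long stay | 1 | 0 | 0 |

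**Step 3: several deaths.** The total change is 0 with no deaths, at most 0.36 with one, and at most 3 × 0.0222/0.0612 = 1.09 with three very early deaths in the same arm. With one early death in each arm, the two moves pull in opposite directions and largely cancel.

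**Step 4: check by simulation.** Assumed inputs, none of them from the SAP: identical lognormal stays in both arms (median about 6 days, log-SD 0.5, rounded up), k deaths on day 2 in one arm, 45 per arm, 3,000 runs. The table shows the mean probability of a longer stay in the arm with the deaths.

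| k | As the SAP is written | Death takes the worst rank | Gap |
|---|---|---|---|
| 0 | 0.500 | 0.500 | 0 |
| 1 | 0.490 | 0.512 | 0.022 |
| 2 | 0.478 | 0.522 | 0.044 |
| 3 | 0.465 | 0.532 | 0.067 |

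The gaps agree with k × 0.0222. As written, the arm with the deaths appears to have shorter stays; under the worst-rank rule the direction reverses. About half of each gap is departure from 0.50 under the SAP's wording. With three deaths this is (0.500 − 0.465)/0.0612 = 0.57 in z.

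**Step 5: would it arise at all?** For an assumed in-hospital mortality p, the chance of at least one death among 90 patients is 1 − (1 − p)⁹⁰: 0.60 at 1%, 0.84 at 2%, 0.94 at 3% and 0.99 at 5%. At 1%, the chance of no death is therefore about 0.40.

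**The case against.** The best defence is that item 7 is an ordinary count of bed-days. It is internally consistent, and no sentence in the SAP calls a death a good result. The ordering is wrong only if stay is read as a measure of recovery. Details may also stand in the protocol, which is not at hand. This has some force, and it rules out saying that the SAP contradicts itself. It does not remove the point: the SAP itself defines the endpoint, picks the test and fixes the population, and together these already return a favourable value for a patient who dies early.

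The objections on size stand in full. The SAP gives no mortality figure. Section 4.2 restricts entry to nonmetastatic disease and excludes several serious cardiac conditions, so no deaths at all is a plausible outcome. The 0.36 is a ceiling that only a very early death reaches. Length of stay is one of 45 listed secondary outcomes, which section 3.1 treats as hypothesis-generating.

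A reader might infer that one or two deaths would overturn the length-of-stay result. The figures do not support that. Even three very early deaths in one arm shift z by about 1.1 between the two scoring rules, short of the 1.96 needed to turn an exactly null result significant. A result would change only if it already lay near the threshold. A reader might also infer that deaths would go unreported. Sections 4.3, 4.4 and 5.5 report losses, withdrawals and adverse events, so some coverage is implied, although death is not named.

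Finally, worst-rank scoring is not the only defensible rule. It changes the estimand from bed-days to a composite of stay and death. That cost is real and is met in the fix.

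**Conclusion.** The point holds as a minor one. Under the SAP's definition, test and population, an early in-hospital death enters the Mann-Whitney comparison as a short, favourable stay, and no other section corrects this. The same is not true of every in-hospital death, since one after a long stay already ranks as long.

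With 45 per arm and an assumed 0 to 3 in-hospital deaths, re-scoring moves z by 0 to at most about 1.1. The upper end requires three deaths, all very early and all in one arm. With no deaths nothing changes. The calculation concerns length of stay only and says nothing about the primary CCI comparison.

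**What to change.** Add one sentence to SAP section 5.1, item 7, before the final analysis: patients who die before discharge are given the worst (longest) rank, tied with one another, in the Mann-Whitney comparison of length of stay. Report the number of in-hospital deaths by arm beside the median stay. Because the ranked endpoint then combines stay and death, also show the plain bed-day summary by arm, so that readers can see resource use separately.

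The cost is one sentence and one extra line in a table. The medical records already used for these outcomes should supply what is needed, so no new data collection is involved, and the test stays the same. If the team prefers time to discharge alive with death as a competing event, stating that in advance would also settle the point, but section 5.2 would then need a different method for this outcome.
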